9.3 VARIABLES

9.3.1 Exposures

Having at least one prescription of either dabigatran or warfarin defined by ATC code or generic name.

9.3.2 Outcomes

9.3.2.1 Primary Outcome

- Outcome name: stroke and systemic embolism
- Time frame: drug exposure period
- Safety issue. N/A
- Definition: definition of stroke and systemic embolism provided in Koretsune et al will be used for this study⁸ as following.
 - ✓ Stroke: all three following conditions must be met:
 - [1] Imaging (magnetic resonance imaging (MRI) or computed tomography (CT)) is performed after a diagnosis code of atrial fibrillation.
 - [2] Diagnosis of stroke defined as I60-I64 occurs in the same month as the imaging
 - [3] Either of the following condition is met:
 - A) Rehabilitation for cerebrovascular disease within 30 days from the date of imaging
 - B) Death within 30 days from the date of imaging
 - ✓ Systemic embolism events:
 1. Retinal vascular occlusions: three following conditions must be met:
 - [1] Ophthalmic examination is performed after the date of definitive diagnosis of atrial fibrillation or cardioembolic stroke (including the day of the diagnosis).
The second or later ophthalmic examination during the same hospitalization is excluded.
 - [2] Diagnosis of retinal vascular occlusion in the month of the date of ophthalmic examination.
 - [3] The following A) and B) are satisfied:
 - A) Prescription of anticoagulant/antiplatelet agents on the day of ophthalmic examination or the next day
 - B) Non-prescription of anticoagulant/antiplatelet agents within 30 days from the date of ophthalmic examination.
 2. Other than retinal vascular occlusions: four following conditions must be met:
 - [1] Imaging: MRI, CT, roentgenography (using a contrast medium) or vascular echo is performed after the date of definitive diagnosis of atrial fibrillation or cardioembolic stroke (including the day of the diagnosis).
 - [2] Systemic embolism (including the name of injury/disease at the time of admission) is diagnosed and recorded as the name of the disease during hospitalization in the month of the date of imaging.
 - [3] The date of imaging or the next day: Treatment
Either of the following conditions is satisfied:
 - A) Treatment with heparin at >5,000 units or thrombectomy on the day of imaging or the next day
 - B) Death within 30 days from the date of imaging

✓ [4] Fees for emergency medicine administration or specific intensive care management on the day of imaging are calculated.

Intracranial bleeding: all four following conditions must be met:

Condition [1] is applied to the events occurred during the hospitalization after the day of definitive diagnosis of atrial fibrillation and is not applied to those during re-hospitalization.

[1] Medical history (only atrial fibrillation)

The following injury/disease name in ICD 10 does not occur in the month prior to the month of the date of definitive diagnosis:

- Cerebrovascular disease excluding sequelae of subarachnoid hemorrhage, sequelae of intracerebral hemorrhage, sequelae of stroke not specified as hemorrhage or infarction
- Intracranial injury

[2] Imaging (MRI or CT) is performed after the month of the date of definitive diagnosis of atrial fibrillation or cardioembolic stroke (including the day of the diagnosis).

The second or later imaging during the same hospitalization is excluded.

[3] Disease name

The following disease occurs in the same month as the day of imaging:

- Cerebrovascular diseases excluding sequelae of subarachnoid hemorrhage, sequelae of intracerebral hemorrhage, sequelae of stroke not specified as hemorrhage or infarction
- Intracranial injury

[4] Rehabilitation of stroke

Either of the following conditions is satisfied:

- Rehabilitation for stroke within 30 days from the date of imaging
- Death within 30 days from the date of imaging

See below tables for definition of imaging (Table 2) and other symptoms/diseases/treatment (Table 3).

Table 2 Definition of imaging for primary outcome

| Receipt code | Definition |
|----------------------|---|
| 170011810 | CT imaging (multi-detector computed tomography) |
| 170020110 | MRI imaging (equipment with 1.5+ tesla) |
| 170033410 | CT imaging (multi-detector computed tomography) |
| 170033510 | MRI imaging (equipment with 3+ tesla) |
| 170000810 | Roentgenography (with contrast agent) |
| 160147110, 160147210 | Vascular echo |
| 160150050, 160161710 | |

Table 3

Definition of symptoms/diseases/treatment for primary outcome

| Symptoms/diseases/treatment | Definition | | |
|-----------------------------------|--------------|--|----------|
| | ICD10 code | Receipt code | ATC code |
| Atrial fibrillation | I48 | | |
| Stroke | I61-64 | | |
| Rehabilitation | | 180027410, 180027510 180027610, 180027710 180030810, 180032410 180032510, 180032610 180033910, 180034010 180034110, 180034210 180034310, 180034410 180043430, 180043530 180043630, 180043730 180043830, 180044310 | |
| Cerebrovascular disease | I60-I69 | | |
| Ophthalmic examination | | 160081010, 160081130, 160081450, 160081550, 160183310, 160199310, 160199310, 160199410 | |
| Cardioembolic stroke | I634 | | |
| Retinal vascular occlusion | H34 | | |
| Anticoagulant/antiplatelet agents | | | B01 |
| Systemic embolism | I74 | | |
| Heparin | | | B01B |
| Thrombectomy | I74, I80-I82 | | |

[figure not shown]
Table 3 (cont'd)

| | |
|---|---|
| Emergency medicine administration/ specific intensive care management | 113002610, 113010710 113013810, 115003010 160000210, 190100070 190116310, 190116410 190137810, 190138110 190138210, 190138310 190138410, 190138510 190138610, 190138710 190138810, 190138910 190139010, 190139110 190139210, 190139310 190139810, 190139910 190171910, 190172010 190174410, 190174510 190174610, 190174710 190174810 |
| Sequelae of Subarachnoid hemorrhage | I690 |
| Sequelae of intracerebral hemorrhage | I691 |
| Sequelae of stroke not specified as hemorrhage or infarction | I694 |
| Intracranial injury | S06 |

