8. RESEARCH QUESTION AND OBJECTIVES

The primary objective is to compare the effectiveness (incidence of stroke/SE) in Japanese patients with atrial fibrillation and newly treated with either dabigatran or warfarin.

The secondary objective is to compare safety (incidence of major bleeding) in patients with atrial fibrillation and newly treated with dabigatran and warfarin in the real world Japanese setting using a claims database.

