9.2 SETTING

MDV clinical database is used.

Definition

1. Index date: the date of first oral anticoagulant prescription, namely warfarin or dabigatran
2. Baseline period: 12 months prior to and including the index date
3. Drug exposure period: period of time from index date to the end of drug treatment determined by having continuous record of prescription with less than 14 days of gap in prescription (grace period) or by switching to another OAC (end of index treatment is then considered to occur the day before the prescription of the new OAC)
4. Follow-up period: the day after index date to the earliest of treatment discontinuation, day before switch, end of continuous enrolment in the database, end of study period or death.

Inclusion criteria

1. >18 year-old with confirmed diagnosis of non-valvular atrial fibrillation (NVAF, ICD 10 code I48)
2. New starters of dabigatran or warfarin

Proprietary confidential information © 2017 Boehringer Ingelheim International GmbH or one or more of its affiliated companies

3. No prescription of other OACs for 12 months prior to the index date, defined as the first prescription of OACs (the period is defined as baseline period)
4. Has an index date between 14th of March 2011 to 30 June 2016

Exclusion criteria

1. Having less than 12 months of enrolment prior to the index date
2. Dialysis or kidney transplant recipients in baseline period
3. Having atrial flutter, valvular AF, mechanical valve placement, rheumatic AF, mitral valve prolapse/regurge/stenosis in baseline period
4. Having record of deep vein thrombosis or pulmonary embolism <6 months before AF diagnosis in baseline period

The symptoms, diseases, or treatments in these criteria are defined by ICD-10 code, disease name, or medical care activity name (see Table 1).

Table 1

Definition of symptoms/diseases/treatment for inclusion/exclusion criteria

| Symptoms/diseases/treatment | Definition | | |
|-----------------------------|------------|----------------|--|
| | ICD10 code | Disease name | Medical care activity name |
| Dialysis | - | - | Including “dialysis” |
| Kidney transplant | T861, Z940 | - | - |
| Atrial flutter | - | Atrial flutter | - |
| Valvular AF | - | Valvular AF | - |
| Mechanical valve placement | T820 | - | Including “mechanical valve placement” |
| Rheumatic AF | I05-I09 | - | - |
| Mitral valve prolapse | I340 | - | - |
| Mitral valve regurge | I341 | - | - |
| Mitral valve stenosis | I050, I342 | - | - |

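### The stroke definition sets no event date, requires no new post-index stroke and does not exclude repeat imaging, so a re-scan of a stroke present at treatment start can count as a primary outcome event

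*Combined protocol and SAP*

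**What the plan says.** **Stroke.** Section 9.3.2.1 sets three conditions. The first is CT or MRI performed after an atrial fibrillation code. The second is "Diagnosis of stroke defined as I60-I64 occurs in the same month as the imaging". The third is cerebrovascular rehabilitation, or death, within 30 days of the imaging. The time frame for the outcome is the drug exposure period.

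**Other definitions in the same section.**
- Retinal occlusion: "The second or later ophthalmic examination during the same hospitalization is excluded".
- Intracranial bleeding: "The second or later imaging during the same hospitalization is excluded".
- Non-retinal systemic embolism has no repeat-imaging rule, but it requires that "Fees for emergency medicine administration or specific intensive care management on the day of imaging are calculated".

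**Time windows and eligibility (9.2).** Definition 4 reads "Follow-up period: the day after index date to the earliest of treatment discontinuation", with further end points after that. Definition 2 reads "Baseline period: 12 months prior to and including the index date". Exclusion 1 removes patients "Having less than 12 months of enrolment prior to the index date". No exclusion criterion concerns recent stroke.

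**Matching (9.3.3).** History of stroke or TIA is a yes/no covariate. Table 4 defines it by I60-I64 and G45, so it shares the outcome's stroke codes.

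**The concern.** The primary objective is to "compare the effectiveness (incidence of stroke/SE) in Japanese patients with atrial fibrillation" newly treated with one of the two drugs. An outcome event should therefore be a stroke that arises after treatment starts. The written conditions are anchored to the atrial fibrillation code, the calendar month of imaging and the 30 days after imaging. None is anchored to the index date or to stroke onset.

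Anticoagulation may be started during a stroke admission or shortly after it. If a later scan of that same stroke counts, a stroke that preceded treatment enters the primary rate and hazard ratio at the very start of follow-up. Equal miscounting in the two arms pulls the hazard ratio toward 1. Unequal miscounting can move it either way.

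**Working it through.** **Step 1: a case tested against the text.** A patient with coded atrial fibrillation, 12 months of enrolment and no prior anticoagulant is admitted with a stroke. Warfarin or dabigatran is started during the stay, which sets the index date. The patient is re-scanned some days later in the same month, with rehabilitation under way.

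| Rule | Does the case pass? |
|---|---|
| Eligibility and exclusions (9.2) | Yes; recent stroke is not listed |
| Imaging after an atrial fibrillation code | Yes |
| I60-I64 in the month of imaging | Yes |
| Rehabilitation within 30 days of imaging | Yes |
| Within the exposure and follow-up window | Yes, if the event is dated by the re-scan |
| Repeat-scan rule | None for stroke |

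If *occurs* in the second condition means the month in which the diagnosis first arises, codes carried into later months drop out, but re-scans within the index month still qualify. Because the baseline period includes the index date, the same stroke also sets the stroke-history covariate to yes.

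**Step 2: the plan's event counts.** Inputs from Table 9 and the sentence below it (9.5): 4,421 per arm, 0.40487 years of follow-up, 0.03 events per patient-year, HR 0.716.

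- Person-years per arm: 4,421 × 0.40487 = 1,789.9
- Warfarin events: 1,789.9 × 0.03 = 53.70
- Dabigatran events: 53.70 × 0.716 = 38.45
- Total: about 92.1

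As a check on these inputs, Φ(√(D/4) × ln(1.378/HR) − 1.96) was computed with D = 53.70 × (1 + HR). The table's HR column is not legible, so HRs of 0.5 to 0.9 were inferred. The result is 0.995, 0.971, 0.899, 0.762 and 0.576, against the plan's 0.996, 0.974, 0.905, 0.770 and 0.583. That is close enough to support reading 0.03 as the warfarin rate.

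**Step 3: illustration of impact.** The miscount shares are assumptions, and the ratio of event counts stands in for the HR because person-time is equal in the two arms.

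| Assumed false events | Calculation | HR |
|---|---|---|
| None | 38.45 / 53.70 | 0.716 |
| 0.1% of each arm (4.4 patients) | 42.87 / 58.12 | 0.738 |
| 0.25% of each arm (11.1 patients) | 49.50 / 64.75 | 0.764 |
| One, dabigatran only | 39.45 / 53.70 | 0.735 |
| One, warfarin only | 38.45 / 54.70 | 0.703 |

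For scale, SE(log HR) = √(1/53.70 + 1/38.45) = 0.211, giving a 95% interval of about 0.47 to 1.08 around 0.716. The two equal-miscount shifts are ln(0.738/0.716)/0.211 = 0.14 and ln(0.764/0.716)/0.211 = 0.31 standard errors.

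**Step 4: cost of a later at-risk start (used under the fix).** A delay of 15.2 or 30.4 days removes 10.3% or 20.6% of person-time if everyone is followed for 0.40487 years. It removes 9.8% or 18.6% if follow-up is exponential with that mean. At a constant rate, the 92.1 events fall to 82.7-83.1 or 73.2-75.0. The log-HR interval widens by a factor of 1/√(1 − loss), which is 1.053-1.056 or 1.108-1.122.

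**The case against.** **The outcome already has a post-index window.** Exposure starts at index and follow-up the day after. If the event were dated by the first scan or the diagnosis, the pathway would largely close. This stands in part: the problem depends on dating the event by the re-scan. But the plan names no event date, and conditions two and three are both tied to the imaging, so the imaging date is a natural choice for a programmer. Nothing says that the stroke must be new.

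**The pathway is narrow.** It needs 12 months of enrolment without an anticoagulant, a stroke in the index admission or index month, a post-index re-scan, and rehabilitation or death within 30 days. This stands, and it is why no frequency is claimed.

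**Matching helps.** Stroke history, prior hospitalization, time from diagnosis to treatment and the risk scores should reduce imbalance between arms. They do not remove the false events, and a yes/no history does not separate a stroke in the index admission from one months earlier.

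**A reader might infer that stroke is the only component without protection.** The text does not support that. Non-retinal embolism also lacks a repeat-imaging rule; its fee condition shows acuity, not first occurrence. The prior-disease condition for intracranial bleeding is tied to the definitive atrial fibrillation diagnosis, not to index. The repeat rules that exist cover one hospitalization only. The supportable contrast is that two definitions have a same-hospitalization repeat rule and stroke has none.

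**The cited validation study, or the redacted part of 9.7, may contain more.** Neither can be checked. The point rests on the stroke definition as written out in the protocol.

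**Conclusion.** The point holds and should be fixed; confidence is medium. As written, a post-index re-scan of a stroke from the index admission or index month meets all three stroke conditions and, if the scan dates the event, places a pre-treatment stroke in the primary hazard ratio. The rule can return a wrong result; this is more than missing detail.

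The size is unknown. The HR shifts above rest on assumed shares and are small against sampling error. With about 92 expected events, however, each net false event moves the estimate by about 0.01 to 0.02.

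A reader might infer that the hazard ratio is biased in a known direction, or that a non-inferiority conclusion is at risk. The documents support neither. They give no miscount rate by arm, and 9.5 plans no formal hypothesis test. The concern is limited to bias in the reported rates and hazard ratio.

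**What to change.** **In 9.3.2.1:**
1. Define the stroke event date as the first qualifying scan of a hospitalization (CT or MRI with an I60-I64 diagnosis in the same month), and require that date to fall in the follow-up period.
2. State that later scans in the same hospitalization for the same I60-I64 diagnosis are not new events. Scans unrelated to a stroke diagnosis must not count as the earlier scan: the CT and MRI codes in Table 2 carry no body region, so an unrelated scan could otherwise delete a genuine in-hospital stroke.
3. Do not count a scan in the index admission or index month when I60-I64 was already recorded on or before the index date.
4. Report by arm the number of events set aside. This would also show how common the problem is.

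**In 9.7.1**, add one sensitivity analysis. If diagnoses carry day-level dates, exclude patients whose I60-I64 code in the index admission or index month is dated on or before index, and re-match. If diagnoses are dated only to the month, start at-risk time in both arms after the index month and any index admission, and re-check covariate balance among those still at risk. The protocol should state which date resolution applies.

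**Cost.** Protocol wording, a few programming conditions and one extra run on data already held. Some genuine early or in-hospital recurrent strokes are lost, and the 74% positive predictive value quoted in section 7 no longer applies exactly. With month-level dates, an unrelated scan earlier in the month of a stroke may still be hard to tell from the first stroke scan. The delayed start, if needed, loses roughly 10% of person-time for an average half-month delay and 19-21% for a full month, and more after an index admission. The interval then widens by about 5-6% or 11-12%. That loss falls on the sensitivity analysis only.

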9.4 DATA SOURCES

MDV clinical database is health insurance claim database. As of end of February 2016, MDV has accumulated commercial claims database for both in and outpatients consisting of medical administrative claims records from more than 12.94 million patients from 230 large acute care DPC hospitals. Lab results are also available but number of hospitals providing with lab test results are limited.

Study period is from 14 Mar 2010 to 30 June 2016 in MDV database at the time of study protocol approval.

The MDV database is broadly representative of the Japanese population with similar distribution compared to the Japanese general population. There is research experience using the data, 19 publications, 5 conference presentations (as of Aug 2015).

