9.11 SUBJECTS

The source population is Japanese patients who have claims data in MDV commercial database. In order to have claims in the database, the patients must have received some medical intervention, out or in-patient hospital visit, or pharmacy prescription from the DPC hospitals in Japan. DPC hospitals are large hospitals, often associated with medical schools or government funding, providing both acute and chronic medical care in Japan. Compared to non-DPC hospitals, they tend to provide more specialized, intensive medical care in addition to outpatient primary care tending to chronic disease requiring non-urgent care. MDV database has contractual agreement to receive claims data from approximately 12% of all DPC hospitals in Japan, and the selection is based on the willingness on the side of DPC hospitals to receive either financial compensation or data services from MDV. The inclusion and exclusion criteria are intended to select those Japanese atrial fibrillation patients who have non-valvular etiology and have newly initiated oral anti-coagulants for stroke prevention. The data cut-off of 14 Mar 2011 to 30 June 2016 is to select those claims that have occurred after the launch of dabigatran and to the most recent available data cut from MDV at the time of protocol writing.

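### Time at risk runs to the last day of data, but a stroke may need up to 30 further days to be confirmed, so incidence is slightly understated

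*Combined protocol and SAP*

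**What the plan says.** Section 9.3.2.1 defines stroke by imaging, a stroke diagnosis in the same month, and one of two confirming facts: "Rehabilitation for cerebrovascular disease within 30 days from the date of imaging" or "Death within 30 days from the date of imaging". Condition [4] for intracranial bleeding is the same. For systemic embolism other than retinal occlusion, a patient without heparin or thrombectomy by the next day qualifies only through death within 30 days. The section also sets "Time frame: drug exposure period" for the outcome.

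Section 9.2 ends follow-up at discontinuation, at the day before a switch, or at "end of continuous enrolment in the database, end of study period or death". Inclusion criterion 4 reads "Has an index date between 14th of March 2011 to 30 June 2016". Section 9.4 says "Study period is from 14 Mar 2010 to 30 June 2016 in MDV database", and section 9.11 says that the window extends "to the most recent available data cut from MDV at the time of protocol writing".

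The plan nowhere gives an event date, a look-ahead period after 30 June 2016, or a rule on whether rehabilitation or death after exposure ends can confirm an event imaged during exposure.

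**The concern.** The numerator and the denominator close at different times. A patient on drug through June 2016 adds 30 days of person-time. A stroke imaged on 20 June, with rehabilitation starting on 5 July, has its confirming claim beyond the data and is not counted. The planned incidence rates are therefore biased downwards.

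A related question arises at each patient's own end of exposure, because the time frame does not say whether it governs the imaging, the confirming claim or both. Mean follow-up in Table 9 is only 0.40487 years, so a 30-day window is not negligible beside it. Two programmers could code the rule differently and obtain different event counts.

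**Working it through.** **Inputs.** From Table 9 and the text of section 9.5: follow-up 0.40487 y, so m = 0.40487 × 365.25 = 147.9 days; 4,421 per group; rate 0.03 per patient-year; margin 1.378; assumed HR 0.716. From section 9.2: index dates from 14 March 2011 to 30 June 2016, which is 1,936 days. Assumptions not in the documents: exponential time on drug with mean m, entry either uniform or rising linearly, and confirmation lag uniform over 0 to 30 days.

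**1. Reproduce the plan's figure.** Power = Φ(ln(1.378/HR) × √(D/4) − 1.96), with D = 4,421 × 0.40487 × rate × (1 + HR) and the rate applied to the warfarin arm. The HR column of Table 9 is not legible in the text; values of 0.5, 0.6, 0.7, 0.8 and 0.9 fit. At 0.03 per year they give 0.995, 0.971, 0.899, 0.762 and 0.576, against the stated 0.996, 0.974, 0.905, 0.770 and 0.583. The rows for 0.025 and 0.035 also agree within one percentage point.

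At HR 0.716, D = 4,421 × 0.40487 × 0.03 × 1.716 = 92.1 events and power is 0.8815. If both arms had 0.03 per year, power would be 0.924.

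**2. Person-time in the last 30 days of data.**
- Uniform entry: approximately 30/(1,936 − 147.9) = 30/1,788.1 = 1.7%.
- Linearly rising entry: 30 × (1,921 − 147.9)/(1,936²/2 − 147.9 × 1,936 + 147.9²), which is about 53,190/1,609,600 = 3.3%.

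**3. Events lost at the data cut.** An event imaged u days before the cut is lost with probability 1 − u/30, which averages one half over the window. That gives about 0.8% (uniform entry) to 1.7% (rising entry), or roughly 1 event of the 92 expected (0.8 to 1.5). If no event in the window were confirmed, the loss would be 1.7% to 3.3%.

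**4. Cost of closing time at risk on 31 May 2016.** Events fall to 92.1 × (1 − 0.017) = 90.6 or 92.1 × (1 − 0.033) = 89.1. Power falls from 0.8815 to 0.876 or 0.871.

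**5. End of exposure, only if the confirming claim also had to fall inside it.**
- Person-time in the last 30 days of each patient's exposure: 1 − exp(−30/147.9) = 18.4%, or 30/147.9 = 20.3% if every patient had exactly the mean.
- Events lost under uniform lag: 1 − (147.9/30) × 0.184 = 9.5%. If none were confirmed, the loss would be the full 18.4% to 20.3%.
- Expected events would fall to between 83 and 73, and power to between 0.848 and 0.801.

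**The case against.** Several points on the other side stand.

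- A reader might infer that events late in the data cannot be confirmed at all. That is too strong: 30 days is a maximum, and early rehabilitation or death in June still qualifies.
- A reader might infer bias in the primary hazard ratio. The cut falls on the same calendar date in both arms, and year of starting treatment, with a last category ending 30 June 2016, is in the propensity score (section 9.3.3). A differential effect would need different persistence or confirmation lag by arm, and the documents report neither.
- A reader might take the 20% in step 5 as the expected loss. It depends on a reading that the plan does not state. The 30-day window is anchored to imaging and carries no exposure condition, and claims after discontinuation or switch remain in the database. Nor does stopping the drug at a stroke end exposure that day: discontinuation is counted from the end of supply with a 14-day grace period. A prompt switch is the clearer case.
- A patient indexed on 30 June 2016 distorts nothing, because section 9.2 starts follow-up the next day.
- The study is declared exploratory, and an earlier closing date also discards June events that were properly confirmed. A sensitivity analysis could be argued to suffice.

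None of this removes the mismatch at the data cut. The current text gives no way to confirm a June event whose first qualifying claim comes in July, and incidence rates are a planned output in their own right.

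**Conclusion.** The point holds as a small defect. About 1.7% to 3.3% of person-time has a shortened confirmation window, and about 0.8% to 1.7% of events would be lost under a uniform lag. Both ranges rest on exponential time on drug and uniform to rising entry. The result is a slight understatement of incidence in both arms, with little expected change in the hazard ratio.

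The end-of-exposure question is one of unclear wording, not an established loss. If confirmation had to fall inside exposure, about 10% to 20% of events could be lost. That is an upper range, which remaining supply and grace days would reduce. It shows why the rule should be written down, not what the plan will do.

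The same shortened window applies to patients who leave the database. The documents do not allow that share to be sized.

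**What to change.** **Main change.** In sections 9.2 and 9.4, end time at risk on 31 May 2016 and use claims from 1 to 30 June 2016 only to confirm events imaged by that date. Patients indexed after 31 May contribute no time at risk. They need not be removed from the matched sample, so no rematching is required; the Cox model in section 9.7.1 contains treatment group only.

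**Clarification.** In section 9.3.2.1, state that the imaging date is the event date and must fall in the drug exposure period, and that rehabilitation or death within 30 days confirms the event even after discontinuation or switch. Apply this to stroke, intracranial bleeding and the death limb of systemic embolism. Say also how the 30-day non-prescription condition for retinal occlusion is handled when fewer than 30 days of data follow the examination.

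**Cost.** One date parameter and a few sentences; 1.7% to 3.3% of person-time; power down from 0.8815 to between 0.871 and 0.876. If the sponsor prefers to keep 30 June 2016 for the main analysis, the 31 May closing date should be a stated sensitivity analysis.

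### Two systemic embolism rules in the primary outcome do not work as written: the retinal prescription window and the coding of thrombectomy

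*Combined protocol and SAP*

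**What the plan says.** **Retinal occlusion (section 9.3.2.1, condition [3]).** Two sub-conditions must both hold:
- A: one of these agents is prescribed when the eye is examined or one day later.
- B, which must hold as well: "Non-prescription of anticoagulant/antiplatelet agents within 30 days from the date of ophthalmic examination".

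Table 3 codes the agents for both by one class, "Anticoagulant/antiplatelet agents | | | B01", with no exception. The study drugs are anticoagulants, so they fall in it.

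**When events count.** The outcome has "Time frame: drug exposure period". Section 9.2 defines exposure by continuous prescriptions of the index drug with gaps under 14 days, and ends it the day before a switch to another oral anticoagulant. It also gives "Follow-up period: the day after index date to the earliest of treatment discontinuation".

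**Other systemic embolism (section 9.3.2.1, condition [3]).** Route A is "Treatment with heparin at >5,000 units or thrombectomy on the day of imaging or the next day"; route B is death within 30 days. The Table 3 row reads "Thrombectomy | I74, I80-I82", with the codes in the ICD-10 column and the receipt-code cell empty. Rehabilitation, ophthalmic examination and intensive care fees all have receipt codes in that table, and imaging has them in Table 2.

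**Source.** Section 9.3.2.1 says the definitions come from a cited validation study. Section 7 reports that study's positive predictive value (PPV) for systemic embolism as 26.7%, and as 86.7% after the claims definition was changed. It does not say which version this text reproduces.

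**The concern.** A retinal rule of this kind presumably looks for treatment begun because of the event. Here every patient is already on a B01 drug, because only on-treatment events count. The study drug's own prescriptions can therefore break B, and a routine refill can satisfy A with no new treatment. Because B has no direction and no day limits, two competent programmers could produce different event counts from the same data. The code checks in section 9.8 would not show which reading was meant.

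The thrombectomy route is meant to confirm that a procedure took place on the day of imaging or the next day. A diagnosis code cannot show that.

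Both rules feed the primary outcome. If the text departs from the validated definition, the 86.7% PPV cannot be assumed to carry over.

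**Working it through.** **1. Retinal rule: three readings of B.** Day 0 is the examination.

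- *Forward, days 0 to 30.* The same time phrase in "Death within 30 days from the date of imaging" can only run forward. A needs a B01 prescription on day 0 or 1 and B forbids one on days 0 to 30, so no event can satisfy both.
- *Forward, days 2 to 30.* An event qualifies only if no further B01 prescription follows up to day 30.
- *Backward, days -30 to -1.* An event qualifies only if no B01 prescription was issued in the preceding 30 days.

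**2. Backward reading, start of follow-up.** Follow-up begins the day after the index prescription, so that prescription breaks B on days 1 to 30. Table 9 uses a follow-up of 0.40487 years, taken here as the mean.

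- 0.40487 x 365.25 = 147.9 days.
- Blocked share: 30/147.9 = 20.3%.
- If follow-up times are exponential with that mean: 1 - exp(-30/147.9) = 18.4%.

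**3. Later follow-up.** The documents give no days of supply, so the refill interval k is an assumption. Take steady refills every k days, no late refill, no other B01 drug, and one cycle in mid-treatment. A can be met in two ways: (i) only by a routine refill on day 0 or 1, or (ii) by a new B01 prescription at every event. For k above 30, case (ii) gives k - 30 qualifying days per cycle backward and k - 29 forward from day 2.

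| k (days) | Backward (i) | Backward (ii) | Forward from day 2 (i) | Forward from day 2 (ii) |
|---|---|---|---|---|
| 28 | 0 of 28 | 0 of 28 | 0 of 28 | 0 of 28 |
| 60 | 2 of 60 (3.3%) | 30 of 60 (50%) | 2 of 60 | 31 of 60 |
| 90 | 2 of 90 (2.2%) | 60 of 90 (67%) | 2 of 90 | 61 of 90 |

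Under the backward reading, no day qualifies for any k of 30 or less. Whether 60-day or 90-day refills capture the larger share of days depends on how A is met: 3.3% against 2.2% in case (i), 50% against 67% in case (ii).

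**4. The last cycle differs under the forward reading from day 2.** Take 28-day fills on days 0, 28, 56, 84 and 112, with supply ending on day 140. An examination on day 111 or later has no fill in its days +2 to +30. Days 111 to 139 can therefore qualify: 29 of 139 follow-up days (21%) in case (ii), and 2 days in case (i).

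**5. Other B01 drugs and switches.** Section 9.3.3 lists aspirin, ticlopidine, cilostazol and clopidogrel as concomitant drugs. A continuing antiplatelet refill can break B or satisfy A just as the study drug can. If the event prompts a switch of anticoagulant on day 0, exposure ends the day before, and an event dated at the examination falls outside the time frame. With a switch on day 1 it falls inside.

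**6. Thrombectomy.** Condition [2] already requires the systemic embolism diagnosis, which Table 3 codes as I74. The thrombectomy row lists I74 again, plus I80-I82; Table 1 uses I802 for deep vein thrombosis, so these are disease codes. If diagnoses carry a usable date, the diagnosis itself can meet the thrombectomy route. If they are dated only by month, the route cannot be evaluated for the day of imaging or the next day. Neither case confirms a procedure.

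**The case against.** **The contradictory reading is not the one intended.** A reader might infer that no retinal event can ever be counted. A and B are listed as joint conditions, so a reading that makes them incompatible would normally be rejected, and new treatment with none in the preceding 30 days is coherent. The cited definition may also settle the direction. This stands: the documents support an unclear rule with a contradictory literal reading, not an impossible outcome. The backward reading still collides with the on-treatment time frame.

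**Short refills do not remove retinal events under every reading.** A reader might infer this from the 28-day row. It fails in the last cycle when the window runs forward from day 2. The backward result also rests on assumptions: a late refill within the permitted gap, or counting grace days after the last supply as exposure, would let some days qualify.

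**The thrombectomy row may be incomplete.** A receipt code lost in conversion from PDF cannot be excluded, and a look at the source table would settle it. Diagnosis codes entered for a procedure would still need explaining. Nor does every recorded I74 become an event: conditions [1], [2] and [4] still apply, and the heparin and death routes are unaffected.

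**Separate counts may already be planned.** Section 9.7.1 mentions event numbers for ischemic stroke and major bleeding with the Kaplan-Meier analysis. The abstract plans numbers of observed events more generally and lists stroke and systemic embolism as separate variables, and the table of contents shows redacted entries. No omission can be asserted.

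**The consequence is not shown.** This also stands. The stroke rule is untouched, and the documents give no split between stroke and systemic embolism.

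**Conclusion.** The point holds for both rules, and no visible text corrects either one.

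- **Retinal rule.** It is contradictory if read forward from day 0. On the more plausible backward reading it blocks days 1 to 30, about 20% of the Table 9 follow-up (18% if follow-up times are exponential). Later capture depends on refill timing of the study drug or of concomitant antiplatelets. With steady refills of 30 days or less, none late, and exposure ending with supply, no on-treatment day qualifies on that reading. The 20% is a share of follow-up time for retinal events, not a share of primary events.
- **Thrombectomy.** As shown in Table 3, the route verifies no procedure.

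A reader might infer a biased hazard ratio, or a bias favouring one drug. The documents do not support either: they give no days of supply by drug and no count of systemic embolism, and the comparison of 60-day with 90-day refills reverses with how A is met. The effect on the composite hazard ratio cannot be sized. This should be fixed before the outcome is programmed; it does not invalidate the primary outcome.

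**What to change.** 1. **Thrombectomy.** Define it in Table 3 by procedure receipt codes, as is done for imaging and rehabilitation.
2. **Retinal window.** State the direction and exact days of B, with days 0 and 1 excluded.
3. **Retinal agents.** Apply A and B to newly started B01 agents, meaning agents with no prescription in a stated look-back. Continuing study-drug or antiplatelet prescriptions then neither block B nor satisfy A.
4. **Dating.** State that the event is dated at the examination, and how it is counted when a switch of anticoagulant on day 0 or 1 ends exposure.
5. **Source.** Reconcile both rules with the cited validated definition, state whether the version with PPV 26.7% or 86.7% is used, and list any departure as a limitation.
6. **Reporting.** Give stroke and systemic embolism counts separately by arm, with a stroke-only sensitivity Cox model, unless a redacted section already plans this.

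The cost is a few lines of text, one table row, modest programming, and a count table with one extra model from data already held. The drawback is that the amended retinal rule may have no validated PPV, which must be said openly; the stroke-only model does not depend on it.
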